**Duke IRB Protocol Number: Pro00085179**

**Principal Investigator: [name]**

**Funded by: National Institute of Child Health and Human Development**

**Version Number: v.1.4**

**17 MARCH 2022**

NCT05417607

*Summary of Changes*

Version / Date	Description of changes	Rationale	Date of Approval (iRIS version)
VI.4/17 MAR 2022	1. The protocol analysis section was updated/clarified to reflect the addition of a statistical analysis plan for the project. Primary outcomes, secondary outcomes, and exploratory outcomes were updated to match the plan.	1. The statistical analysis plan, protocol and CT.gov should all be in agreement to prevent any confusion.	
VI.3/12 AUG 2021	2. Removed 16 week physician check in. 3. Clarified that if there is limited internet access participants can receive coaching through telephone and record interactions for both the PCI and ESDM sessions and upload to Duke BOX. 4. Removed language that is not applicable to the protocol (section 6.4.1) - this section previously stated that participants will be asked to refrain from changing the type or intensity of other behavioral interventions during the study. 5. Removed information for [name] as former Co-I for the	2. It does not impact the primary or secondary outcomes for the study and data (missed week 16 physician visits) is suggesting that participants are finding this to be a burden. 3. We would like to ensure that parent coaching and study procedures are accessible to study participants that are unable to obtain high-speed internet access. 3. and 4. – No longer pertinent to protocol. 3. was legacy language and this is a feasibility study so medications and behavioral interventions will not be restricted; if there	20 SEP 2021

	ACE.	is something that seriously impedes participation, then the study PI will take appropriate action to discontinue, withdraw, or provide participant with feedback on options .	
VI.2/16 APR 2021	
1.Primary PI changed from [name] to [name]
 
2.Updated inclusion criterion # 4 to allow for tele-ASD-peds used in clinic and further clarification of diagnostic assessment.
 
3.Removing measures from protocol: CGI-I&S, ADHD-RS (clinician administered), and Sluggish Cognitive Tempo (AOA) questionnaire. Reducing the number of times the ADHD-RS (parent) caregiver completed form is assessed.
 
4.Clarified what measures may need to be repeated if too much time has progressed through the assessment core (see SOA).
 
5. Clarified procedures for conducting Qualitative Interview and consent process with
	
1.[name] has valuable experience to take on the PI role and this change helps balance other PI transitions across the ACE.
 
2.We are including a telehealth assessment that is standard practice being used in younger children during COVID for ASD diagnosis.
 
3.These assessments add additional time burden to the families and we feel that given the remote nature of the study they are not required assessments for primary end goals.
 
4.Clarifying in the table of assessments what may need to be repeated
 
5. The qualitative interview with staff, clinicians, and coaches requires a consent process and outlining of ways we will minimize bias and ensure
	24 APR 2021 (iRIS Version 1.5)

Feasibility trial of adapted ESDM informed caregiver coaching delivered remotely for children with ASD and ADHD

Protocol **Pro00085179, v1.4**

17 March 2022

	stakeholders who are study staff.	voluntariness.	
v1.1 / 28 DEC 2020	Removed exclusion criterion (#5) which was based on presence of known genetic or other neurological condition; modified exclusion #1 to specify CNS active medications (not just ADHD medications) must be stable 4 weeks prior to baseline.	The presence of genetic or neurological condition alone is not expected to affect the suitability or applicability and potential benefit or risk profile of the intervention to children with these characteristics; removal of exclusion makes the sample more representative. It is ideal for all psychotropic medications to not change prior to baseline to reduce possibility of changes in medications/symptoms confounding data.	19 JAN 2021 (iRIS Version 1.3)
v1.0 / 07 DEC 2020	First version, feasibility sub-study	Initiating feasibility sub-study	16 DEC 2020 (iRIS version 1.1)

## STATEMENT OF COMPLIANCE

The study will be carried out in accordance with International Council for Harmonisation Good Clinical Practice (ICH GCP) and the following:

- United States (US) Code of Federal Regulations (CFR) applicable to clinical studies (45 CFR Part 46, 21 CFR Part 50, 21 CFR Part 56, 21 CFR Part 312, and/or 21 CFR Part 812)

National Institutes of Health (NIH)-funded investigators and clinical trial site staff who are responsible for the conduct, management, or oversight of NIH-funded clinical trials have completed Human Subjects Protection and ICH GCP Training.

The protocol, informed consent form(s), recruitment materials, and all participant materials will be submitted to the Institutional Review Board (IRB) for review and approval. Approval of both the protocol and the consent form must be obtained before any participant is enrolled. Any amendment to the protocol will require review and approval by the IRB before the changes are implemented to the study. In addition, all changes to the consent form will be IRB-approved; a determination will be made regarding whether a new consent needs to be obtained from participants who provided consent, using a previously approved consent form.

## 1 PROTOCOL SUMMARY

### 1.1 Synopsis

**A+ Treatment:** Feasibility trial of adapted ESDM-informed caregiver coaching delivered remotely for children with Autism Spectrum Disorder (ASD) and Attention-Deficit/Hyperactivity Disorder (ADHD); Duke Autism Center of Excellence (Duke ACE), Project 3; Protocol Pro00085179, v1.0 23 October 2020)

**Study Description:** This study will evaluate the feasibility of adapted ESDM-informed caregiver coaching in children with comorbid ASD and ADHD, who are between 36 and <132 months of age. There will be no study provided medication treatment in this study. Children will either be on ADHD medication prescribed by their own personal provider or will not be taking any ADHD medication (this will be documented by the study). The provided behavioral treatment will be eight ~60-minute sessions in ESDM-informed caregiver coaching remotely delivered weekly, for 8 consecutive weeks. The behavioral treatment is provided to children through Early Start Denver Model (ESDM)-informed caregiver coaching strategies, implemented within the child's typical daily routine by the caregiver. Pre-baseline procedures included screening and eligibility procedures, cognitive & diagnostic assessments. This was followed by baseline visit (Week 0), 8 subsequent weekly coaching sessions (Weeks 1 - 8), an endpoint visit (Week 9), and a follow up visit (Week 16).

**Objectives:** The overarching goal of A+ Treatment is to evaluate feasibility and gather

pilot data of remotely-delivered ESDM informed caregiver coaching for children with ASD and ADHD which may inform future combination clinical trials (pharmacotherapy and behavioral intervention).

**Primary Endpoint:** Using an implementation science approach we will characterize the acceptability, appropriateness, feasibility and fidelity of remotely behavioral intervention in the following ways: 1. Using 3 pragmatic measures: Acceptability of Intervention Measure (AIM), Intervention Appropriateness Measure (IAM), and Feasibility of Intervention Measure (FIM). 2. Conducting qualitative interviews (caregiver, clinician and staff) of perceptions regarding the intervention. 3. Assessing fidelity of intervention delivery, using adapted ESDM Fidelity rating scales.

**Key Secondary Endpoints** The proximal outcomes of child and caregiver behaviors and sense of competence after the intervention. Key proximal outcomes will be change from baseline (pre-intervention) to 9-weeks (post-intervention) in caregiver sense of competence measured by the Parent Sense of Competence Scale and child behaviors measured by the sum of 4 items from the JERI (Joint Engagement, Attention to Caregiver, Responsiveness to Partner's Communication Bids, Fluency and Connectedness) coded by a trained, reliable coder who is naïve with respect to whether the observation is from baseline our outcome using video-recorded caregiver-child interactions.

**Other Exploratory Endpoints** Additional exploratory outcomes will be change in caregiver ratings from baseline to 9-week in the following measures: a) ADHD-RS ratings of the child's attention; b) Aberrant Behavior Checklist (ABC), including inattention/hyperactivity, social withdrawal, stereotypies, irritability, and inappropriate speech; c) Social Reciprocity Scale-2 (SRS-2) ratings of child's social communication behavior; d) Caregiver Strain Questionnaire (CSQ) ratings of the impact of the child's condition on the family and caregiver and quality-of-life; e) Behavior Rating Inventory of Executive Functions (BRIEF) ratings of child's executive function; and f) Child Behavior Checklist (CBCL) ratings of child behavioral and emotional problems. Change from baseline (pre-intervention) to 16-weeks (8-weeks post-intervention) will be assessed for the VABS-3 Socialization and Communication Subscale Standard Scores.

**Study Population:** ~ 30-35 participants who are between 36 months and <132 months of age with comorbid ASD and ADHD.

- Inclusion criteria**
- Provision of a parent/guardian signed and dated informed consent form.
  - Stated willingness of parent/guardian to comply with all study

procedures and availability for the duration of the study.

- Child is between 36 months and <132 months of age at baseline.
- Child has a confirmed DSM-5 diagnosis of both ASD and ADHD, informed by results of assessments including: an ASD diagnostic assessment (Brief Observation of Symptoms of Autism [BOSA], Autism Diagnostic Observation Schedule, 2nd Edition [ADOS-2], or TELE-ASD-PEDS, and if applicable the Autism Diagnostic Interview - Revised [ADI-R]) and an ADHD diagnostic (a standardized ADHD Diagnostic Interview and the MINI psychiatric diagnostic interview).

**Exclusion Criteria**

- If continuing psychotropic (CNS-active) medications, must not have been changed within 4 weeks prior to baseline
- Significant visual, auditory or motor impairments that would preclude participation in ESDM-informed caregiver coaching or completion of key assessments.
- Inability of the caregiver participating in ESDM-informed caregiver coaching and responding to questionnaires to fluently speak English.
- Study clinician judgment that it is not in the best interests of the participant and/or the study for the child to participate (including presence of psychiatric conditions or psychiatric symptoms in addition to ASD and ADHD that in the opinion of the PI or based on senior clinical review, would confound assessments and/or affect participation in the study).

**Description of Sites**

**Enrolling Participants:** Single academic center site in US.

**Description of Study Intervention:** All participants will receive eight consecutive weekly ~60-minute ESDM-informed caregiver coaching sessions.

**Participant Duration:** Total participation is expected to require a maximum of 20 weeks, including optional remote follow-up at 16 weeks. The A+ Treatment diagnostic and screening visits will generally occur between 1 and 6 weeks prior to baseline. ESDM-informed parent coaching will be delivered per the Schedule of Activities (SOA) for 8 weeks. Endpoint assessments will be completed after the final coaching visit. No medication will be provided by the study team. The final assessment will be obtained at 16 weeks after baseline.

1.2 Schema

**Figure 1: A+ Treatment Schema** A+ Treatment staff will meet with parents/caregivers to explain the study and to review the informed consent document with them. Eligibility in the A+ Treatment study will include meeting diagnostic and age criteria. ESDM-informed caregiver coaching begins after baseline assessments and will continue for 8 weeks. The primary outcome assessments will evaluate feasibility of ESDM-informed caregiver coaching in children ages 3-10. This study will be conducted remotely.

Week -2 to -1	Week 0	Weeks 1-8	Week 9	Week 16
Screen & Confirm Diagnose	Baseline	ESDM Sessions	Endpoint	Remote Follow-up
Diagnostic assessments Cognitive testing Parent questionnaires Vineland-3 parent report	Joint engagement Social communication ADHD symptoms AIM Parent questionnaires	ESDM Caregiver Fidelity ESDM Caregiver Self-Monitoring ESDM Coaching Fidelity	Joint engagement Social communication ADHD symptoms AIM Qualitative interview Vineland-3 parent report Parent questionnaires	Social communication ADHD symptoms Parent Questionnaires Vineland-3 parent report

### 1.3 Schedule Of Activities (SoA)

ACTIVITIES	Consent & Diagnostic Confirmation a & Feedback	Baseline/and call with Coach	Coaching W1	Coaching W2	Coaching W3	Coaching W4	Coaching W5	Coaching W6	Coaching W7	Coaching W8	Endpoint Assessments	Remote Follow-up
Typical Week offset from baseline A	prior	0	1	2	3	4	5	6	7	8	9	16
Informed consent	X											
Demographics, ACE subject Med Hx, ACE Fam Hx, Intervention Hx,  Spence	X											
Diagnostic & Cognitive testing	X											
ESDM-informed caregiver coaching		Brief call	X	X	X	X	X	X	X	X		
P-ESDM Caregiver Self-Monitoring checklist**			X	X	X	X	X	X	X	X		
ESDM coach fidelity *			*	*	*	*	*	*	*	*		
ESDM caregiver fidelity		X	X	X	X	X	X	X	X	X	X	
Remote PCIT												
JERI coding of child/ caregiver items		X									X	
Qualitative Interview											X	
AIM, IAM, FIM											X	
Caregiver Sense of Competence Scale		X									X	X
App S2K		X									X	X
ABC		X					X				X	X
Vineland-3 parent questionnaire	X										X	X
CBCL	X										X	X
ADHD-RS-parent	X										X	X
SRS-2	X	(X) +									X	X
Caregiver Strain Questionnaire		X									X	X
Condensed (non-ASD) Med Hx  , AE's, Con Meds,		X	X	X	X	X	X	X	X	X	X	
BRIEF	X	(X) +									X	

A: no strict window for visits, but ideally post-baseline visits should be done within ± 7 days (relative to visit each time point from baseline); \*: done once randomly

during sessions 2-8; \*\*: completed by caregiver and coach; **Green text: measures acquired in ARC and in P3**; (X)+: only needs to be done if baseline done more than 3 months prior; 2: non ASD med history only done at baseline visit & diagnostic confirmation is informed by ARC assessments. Participants typically begin study participation within 1-3 months of completing the ARC evaluation (if the participant is eligible). However, we also expect that in some situations, (e.g., due to the COVID-19 pandemic) there may be a delay between the ARC evaluation and participation in the A+ Treatment/Feasibility sub-study. If this happens, the following assessments and/or parent-report forms may be repeated:

- If > 2 years since ARC completion: ASD diagnostic assessment (e.g., BOSA, ADOS, TELE-ASD-PEDS) and cognitive assessment (e.g., WPPSI/WISC, DAYC-2, DAS-2, Mullen)
- If > 6 months since ARC completion: CBCL
- If > 3 months since ARC completion of: SRS-2, VABS, ADHD-RS parent form

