### 5.2 Exclusion Criteria

An individual who meets any of the following criteria will be excluded from participation in this study:

1. If continuing psychotropic (CNS-active) medications, must not have been changed within 4 weeks prior to baseline.
2. Significant visual, auditory or motor impairments that would preclude participation in ESDM-informed parent coaching or completion of key assessments.
3. Inability of the caregiver participating in ESDM-informed caregiver coaching and responding to questionnaires to fluently speak English.
4. Study clinician judgment that it is not in the best interests of the participant and/or the study for the child to participate (including presence of psychiatric conditions or psychiatric symptoms in addition to ASD and ADHD that in the opinion of the PI or based on senior clinical review, would confound assessments and/or affect participation in the study).

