## 6.3 Measures to Minimize Bias: Randomization And Blinding

*All participants will be treated openly with caregiver coaching with no randomization occurring and no blinding occurring. If participants choose to take ADHD medications that will be done separately from the study with no randomization or specific rules for treatment.*

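### Section 9.3.8 prescribes between-group tests in a single-arm study; secondarily, the baselines of ADHD-RS, Vineland-3 and CBCL can predate the 4-week medication-stability window, and Section 9 does not use the medication data

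*Combined protocol and SAP*

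**What the plan says.** **Tests.** Section 9.3.8 lists ADHD-RS, ABC, SRS-2, Caregiver Strain Questionnaire, BRIEF and CBCL. It bases inference on between-group t-tests, or Mann-Whitney tests if assumptions fail, after stating that graphics come first. The Synopsis and Section 2.3 define the same outcomes as change from baseline to week 9, with Vineland-3 (VABS-3) to week 16. Under Section 6.1.3 every family receives the same intervention, and Section 6.3 rules out randomisation. Section 9.3.3 gives paired t-tests or the Wilcoxon signed-rank test for pre-post change, with a Vineland-3 score among its examples. Section 9.3.7 makes any subgroup analysis non-inferential.

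**Baselines.** In the Schedule of Activities (Section 1.3), ADHD-RS, Vineland-3 and CBCL are marked in the pre-baseline diagnostic column and have no week-0 cell. The notes say: "Participants typically begin study participation within 1-3 months of completing the ARC evaluation". If there is a delay, "the following assessments and/or parent-report forms may be repeated", with the triggers "If > 3 months since ARC completion of: SRS-2, VABS, ADHD-RS parent form" and "If > 6 months since ARC completion: CBCL". SRS-2 and BRIEF have a conditional week-0 cell: "only needs to be done if baseline done more than 3 months prior".

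**Medication.** Section 5.2: "If continuing psychotropic (CNS-active) medications, must not have been changed within 4 weeks prior to baseline". The v1.1 entry in the Summary of Changes explains this rule as protection against confounding by medication changes. Section 6.3: "If participants choose to take ADHD medications that will be done separately from the study with no randomization or specific rules for treatment". Section 8.1 provides a medication list at baseline and a log at weeks 1-9.

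**The concern.** A between-group test needs two groups, and the plan defines none. An analyst following Section 9.3.8 would have to invent a split, or treat the baseline and follow-up scores of the same children as independent samples. Neither answers the stated question of change from baseline.

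The baseline issue affects how the pilot change scores are read. The stability rule protects the 4 weeks before week 0. If the rating used as baseline was made earlier, a medication change between the rating and that window is compatible with eligibility and becomes part of the change score. This matters most for ADHD-RS. Section 2.2 sees no sign that behavioural treatment acts directly on ADHD symptoms, and it cites a parent-rated methylphenidate effect of 0.66. The pilot is meant to inform a trial combining medication with behavioural treatment, where the two sources of change must be told apart.

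**Working it through.** There is no power or precision figure to reproduce: Section 9.1 bases the sample size on recruitment.

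**1. Does the prescribed test fit the design?**
- Groups available: one (Sections 6.1.3 and 6.3).
- Quantity of interest: within-child change (Synopsis, Section 2.3).
- Test in Section 9.3.8: between groups. Test in Section 9.3.3: paired.
- The one natural split in the documents is on versus not on ADHD medication (Synopsis, Section 6.1.1). Section 9.3.8 does not name it, and inferential testing of it would conflict with Section 9.3.7.
- If baseline and week-9 scores were entered as two independent samples with equal SDs, the standard error in SD units would be √(2/n) instead of √(2(1−r)/n), a ratio of 1/√(1−r). With an assumed pre-post correlation r, this is 1/√0.5 = 1.41 at r = 0.5 and 1/√0.3 = 1.83 at r = 0.7.

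**2. How much time does the 4-week rule leave uncovered?**
One month = 365.25/12/7 = 4.35 weeks. Gap = max(0, rating age − 4 weeks).

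| Age of rating at week 0 | Weeks | Gap (weeks) | Rating to week 9 (weeks) |
|---|---|---|---|
| Schema, earliest (week −2) | 2.0 | 0 | 11.0 |
| 1 month | 4.3 | 0.3 | 13.3 |
| 3 months | 13.0 | 9.0 | 22.0 |
| 6 months (CBCL) | 26.1 | 22.1 | 35.1 |

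For Vineland-3 to week 16, a 3-month-old rating gives 13.0 + 16 = 29.0 weeks. The 3- and 6-month rows are not maxima. Repeats beyond them are discretionary for ADHD-RS, Vineland-3 and CBCL, and the clock runs from ARC completion, not from the rating date.

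**3. Illustration for ADHD-RS only.**
Suppose a fraction g of children start medication in the gap and gain 0.66 SD. The mean change shifts by 0.66 × g: 0.03, 0.07 or 0.13 SD for g = 5%, 10% or 20%.

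The 95% CI half-width for mean change is t(0.975, n−1) × √(2(1−r)/n). With n = 30:
- r = 0.7: 2.045 × √(0.6/30) = 0.29 SD
- r = 0.5: 2.045 × √(1/30) = 0.37 SD

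So g = 20% equals 0.132/0.289 = 46% or 0.132/0.373 = 35% of the half-width. For g = 5% the figures are 0.033/0.289 = 11% and 0.033/0.373 = 9%. Both g and r are assumptions. The 0.66 comes from school-age children with ADHD, and stopping medication would push the other way. The documents give no corresponding effect for the other scales.

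**4. Is the medication information used?**
Sections 9.1 to 9.3.8 contain no descriptive, stratified or sensitivity analysis by medication. The baseline descriptives in Section 9.3.5 do not list it. Section 9.3.4 mentions medication only to say that the study provides none.

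**The case against.** The case on the other side has force on the baseline point.

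- **SRS-2 and BRIEF.** A reader might infer that every exploratory rating can be arbitrarily old. The documents do not support that. The conditional-cell note calls for a week-0 repeat of SRS-2 and BRIEF after 3 months, even though the footnote also lists SRS-2 among the optional repeats. Section 8 says the SRS is obtained at baseline, and ABC and Caregiver Strain have week-0 cells.
- **The schema.** Section 1.2 puts screening, including Vineland-3, at week −2 to −1 and shows entries for ADHD symptoms and social communication at week 0. It names no instrument for those entries, so it does not prove that ADHD-RS is re-rated. It does make this partly an inconsistency between sections. The colour key in the Schedule was also lost in extraction, which limits what can be said about which forms are collected again in this study.
- **Synopsis interval.** The 1-6 weeks given there may describe study visits only and need not conflict with a 1-3 month lag after ARC.
- **Open medication use.** It is tempting to call this a flaw. It is a stated choice: "this is a feasibility study so medications and behavioral interventions will not be restricted".
- **Unseen SAP.** Section 9.3.1 promises a final plan before database lock, and its subgroup list is open-ended. It may already cover medication.
- **Low stakes.** The outcomes are exploratory, Section 4.2 disclaims efficacy, and a single-arm change cannot be attributed to coaching in any case. Medication changes after week 0 can affect the week-0 measures too.

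These arguments reduce the baseline point to a reporting improvement. They do not rescue Section 9.3.8. Even if it meant a medication-status comparison, it defines no groups and conflicts with Section 9.3.7.

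**Conclusion.** The between-group tests in Section 9.3.8 are wrong as written and should be corrected however old the baselines prove to be.

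The baseline point holds for ADHD-RS, Vineland-3 and CBCL, and for SRS-2 and BRIEF only up to 3 months. About 9 weeks are uncovered for a 3-month-old rating and about 22 for a 6-month-old CBCL; a rating no more than 4 weeks old has no gap. The number of children affected is unknown. No size of bias is claimed beyond the ADHD-RS illustration, which rests on assumed g and r and a borrowed effect size.

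A reader might infer that the study's main results are compromised. They are not: the primary outcomes do not depend on these ratings, and the secondary outcomes (Sense of Competence and JERI) have week-0 ratings. Nor can it be said that the medication data will go unused, only that Section 9 as supplied does not use them.

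**What to change.** 1. In Section 9.3.8, replace the between-group tests with the paired t-test or Wilcoxon signed-rank test of Section 9.3.3 for pre-post change. If a comparison by ADHD medication status was intended, define the groups and report it descriptively only, as Section 9.3.7 requires.
2. In the final SAP, name the rating that serves as baseline for each exploratory outcome. Report its age at week 0 (median, range, number older than 4 weeks).
3. Report change scores overall and, descriptively, in children with no recorded start, stop or change of CNS-active medication between the baseline rating and the outcome. Show unknown dates as a separate category.
4. Reconcile the schema (screening at week −2 to −1 with Vineland-3; ADHD symptoms and social communication at week 0) and the SRS-2 text in Section 8 with the Schedule of Activities.

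No medication rule is proposed.

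**Cost.** Items 1, 2 and 4 are mainly text and reporting. Item 3 needs medication dates for the ARC-to-week-0 gap and, for Vineland-3, for weeks 9-16, because the baseline list records current medication and the log stops at week 9. For children already enrolled, the gap dates would be retrospective. That could be many: at the planned 1-3 per month, the 15 months from December 2020 to March 2022 project to 15 × 1 = 15 up to the full target of 30-35. The unchanged subset is also less precise. With 10% or 30% of 30 children flagged, 27 or 21 remain, and the half-width from step 3 of the working grows from 0.29 to 0.31 or 0.35 SD (r = 0.7), or from 0.37 to 0.40 or 0.46 SD (r = 0.5).
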